[Part 2 of 2 of the document. The other parts are not shown.]

Please see the Recommendations of the Adult AIDS Clinical Trial Group Cardiovascular Disease Focus Group [Dube, 2003] for full discussion of management of hyperlipidemia in the context of HIV therapy.

#### **7.4.5.4. Seizures**

A small number of seizure cases have been reported following CAB administration (less than 1% of all those receiving CAB in clinical studies).

. These cases have had alternative explanations for their occurrence.

ViiV Healthcare has reviewed these cases in detail and does not believe they constitute a reasonable likelihood of causation associated with CAB. This assessment is supported by the lack of preclinical signal, class effect or known CNS mechanism, the relatively low frequency of seizures relative to expected rates in both healthy and HIV positive participants and clinical confounders in each case. The Sponsor considers the risk of developing seizures on the study as being no higher than that of the rest of the HIV-1 infected population.

Seizures that occur on study should be managed according to the local guidelines on emergency seizure management which may include treatment with benzodiazepines, general supportive treatment, exclusion of metabolic and toxicological abnormalities

using laboratory tests, septic workup and excluding underlying structural abnormalities with neuroimaging.

Where seizures occur, the Sponsor would like to better characterize these occurrences to enable systematic analyses.

Investigators are requested to document and report seizure or possible seizure events promptly (within 24 hours of learning of the event) to the Sponsor for evaluation and onward reporting. Data should be documented on the appropriate eCRF seizure page.

#### **7.4.5.5. Creatine Phosphokinase (CPK) Elevation**

A Grade 3 or higher elevation in CPK should result in a repeat assessment within 2-4 weeks to ensure the result is transient or due to exercise and will not require a change in study treatment. A history regarding use of drugs known to cause increase of CPK (such as statins) physical activity or exercise preceding the CPK evaluation should be obtained.

Grade 4 elevations in CPK should have a repeat assessment after the participant has abstained from exercise for >24 hours. For persistent Grade 4 CPK elevations that are considered possibly or probably related to the IP, IP should be discontinued and the participant withdrawn from the study. Any participant receiving at least one dose of CAB LA and /or RPV LA who discontinue IP / Withdraw will initiate treatment with HAART enter the LTFU Phase for 52 weeks of follow-up.

#### **7.4.5.6. Lipase Elevations and Pancreatitis**

Participants with asymptomatic Grade 1 or 2 elevations in lipase may be followed closely for the development of symptoms.

Participants with asymptomatic Grade  $\geq 3$  elevations in lipase that are considered possibly or probably related to IP should have IP interrupted until serum lipase returns to Grade  $\leq 2$ . The lipase assay should be repeated within 2 weeks of any Grade  $\geq 3$  result. Participants with persistence of Grade  $\geq 3$  lipase in the absence of other diagnoses or reoccurrence of lipase elevation (at Grade  $\geq 2$ ) following reintroduction of IP should permanently discontinue IP.

Participants with a confirmed diagnosis of clinical pancreatitis that is considered possibly or probably related to IP should have IP held. After complete resolution of the episode, participants may be re-challenged with IP after discussion with the Medical Monitor, only if the Investigator has compelling evidence that the event was not caused by IP. Upon re-challenge, lipase determinations should be performed every 2 weeks for at least 6 weeks after re-initiation of treatment. With any elevation of lipase of Grade  $\geq 2$  or any recurrence of symptoms, the participant should discontinue IP and be withdrawn from study.

Any participant receiving at least one dose of CAB LA and /or RPV LA who discontinue IP / Withdraw will initiate treatment with HAART and enter the LTFU Phase for 52 weeks of **follow up**.

***Drug Restart Following Transient Resolving Liver Events Not Related to Study Drug***

Approval by VSLC for drug restart can be considered where:

Liver chemistries have a clear underlying cause (e.g., biliary obstruction, hypotension, and liver chemistries have improved to normal or are within  $1.5 \times$  baseline and  $ALT < 3 \times ULN$ ). Ethics Committee or IRB approval of drug restart must be obtained, as required.

If restart of drug is approved by VSLC in writing, the participant must be provided with a clear description of the possible benefits and risks of drug administration, including the possibility of recurrent, more severe liver injury or death.

The participant must also provide signed informed consent specifically for the restart. Documentation of informed consent must be recorded in the study chart.

Study drug must be administered at the dose specified by VSLC.

Participants approved by VSLC for restarting study drug must return to the clinic once a week for liver chemistry tests for a minimum of one month and thereafter for as long as clinically indicated and then laboratory monitoring may resume as per protocol. If protocol defined stopping criteria for liver chemistry elevations are met, study drug must be stopped.

Refer to Section 11.2, U.S. Department of Health and Human Services, National Institutes of Health, National Institute of Allergy and Infectious Diseases, Division of AIDS. Division of AIDS (DAIDS, 2017) Table for Grading the Severity of Adult and Pediatric Adverse Events, Version 2.1. [March 2017]. Available from: <https://rsc.tech-res.com/docs/default-source/safety/daids-ae-grading-table-mar2017.pdf>

Refer to Section 11.3, Appendix 3: Liver Safety – Required actions, Follow up Assessments and : Liver Safety – Study Treatment Restart Guidelines for further details.

**7.4.5.7. Decline in Renal Function**

Participants who experience an increase in serum creatinine from Baseline of 45 micromoles/liter ( $\mu\text{Mol/L}$ ) (or 0.5 milligrams/deciliter [ $\text{mg/dL}$ ]) should return for a confirmatory assessment within 2 to 4 weeks. A urinalysis and urine albumin/creatinine and urine total protein/albumin ratios should also be done at this confirmatory visit. If the creatinine increase is confirmed, the investigator should contact the study medical monitor to discuss additional follow-up and medical management.

Participants who have a decline in the estimated GFR (using the CKD-EPI method) of  $>50\%$  from Baseline must return for a confirmatory assessment as soon as possible [Levey, 2009]. A urinalysis and urine albumin/creatinine and urine protein/creatinine ratios should also be done at this confirmatory visit. If the estimated GFR has declined by  $>50\%$  (confirmed), then study drug should be withheld and the investigator should contact the study medical monitor to discuss the rationale for restarting study drugs (if appropriate). Consideration for confounding factors (e.g., background therapy, other

medications, dehydration, concurrent conditions) should be taken into account, and a nephrology consult may be obtained.

#### **7.4.5.7.1. Proximal Renal Tubule Dysfunctions (PRTD)**

PRTD is defined as:

Confirmed rise in serum creatinine of  $\geq 0.5$  mg/dL from Baseline AND serum phosphate  $< 2.0$  mg/dL;

Either of the above accompanied by any two of the following:

Glycosuria ( $\geq 250$  mg/dL) in a non-diabetic;

Low serum potassium ( $< 3$  mEq/L);

Low serum bicarbonate ( $< 19$  mEq/L).

Participants meeting criteria for PRTD must return for a confirmatory assessment within 2 weeks of diagnosis. A urinalysis should also be performed at the time of the confirmatory assessment. If PRTD is confirmed participants should have study drug withheld and the investigator should contact the Study medical monitor to discuss the rationale for restarting study drugs (if appropriate). Consideration for confounding factors (e.g., NRTI backbone, other medications, dehydration, concurrent conditions) should be taken into account, and a nephrology consult may be obtained. If study drug is reinitiated, it should have been withheld for no more than 4 weeks.

#### **7.4.5.8. Proteinuria**

Participants with an abnormal urine microalbumin/creatinine ratio ( $> 0.3$  mg/mg,  $> 300$  mg/g, or  $> 34$  mg/mmol) that represents a change from Baseline and no associated increase in creatinine, should have a repeat spot urine microalbumin/creatinine ratio performed within 2-4 weeks. If confirmed, then consideration should be given to additional evaluation after consultation with the study medical monitor. Additional evaluation may include a 24-hour urine protein and creatinine measurement and nephrology referral.

Participants with an abnormal urine albumin/creatinine ratio ( $> 0.3$  mg/mg,  $300$  mg/g, or  $> 34$  mg/mmol and representing a change from Baseline) and a serum creatinine increase  $> 45$   $\mu\text{mol/L}$  (or  $0.5$  mg/dL) should have confirmation of both results within 2 weeks. If confirmed, the study medical monitor should be contacted immediately. Agreement on further management should be agreed between the investigator and medical monitor.

#### **7.4.5.9. QTc Prolongation**

Participants with an average QTc interval  $> 550$  msec from three or more tracings separated by at least 5 minutes should have IP discontinued. These criteria are based on an average QTc value of triplicate ECGs. If an ECG demonstrates a prolonged QT interval, obtain 2 more ECGs over a brief period ( $\sim 5$ -10 minutes) and use the averaged QTc values of the 3 ECGs to determine whether the participant should be discontinued

from the study. If an alternative cause of the QT prolongation is determined (e.g., participant receiving drug known to cause prolonged QT or TdP), then IP may be restarted after consultation with, and agreement by, the Medical Monitor.

#### **7.4.5.10. Injection Site Reactions (ISRs)**

Injection site reactions will be managed through investigator assessment throughout the study. All ISRs that are either serious, Grade 3 or higher, or persisting beyond 2 weeks must be discussed with the Medical Monitor to determine etiology and assess appropriate continued study participation.

Digital photographs may be documented where possible on all participants who have an injection site reaction, with observable findings, that is either serious or Grade 3 or higher, or that persists beyond 2 weeks. Dermatology will be consulted on all participants who have an injection site reaction considered serious, Grade 3 or above, or if clinically significant and persistent beyond 30 days and others if the Investigator or Medical Monitor feels it is medically necessary.

Details regarding photo collection and any other follow up will be given by the Medical Monitor at the time of assessment.

ISR discomfort can be managed symptomatically (e.g., cold/warm compress, acetaminophen, ibuprofen) if the reaction is interfering with the participant's ability to perform activities of daily living. The required intervention should be documented on the appropriate eCRF page.

#### **7.4.5.11. Allergic reaction**

Participants may continue study drug for Grade 1 or 2 allergic reactions at the discretion of the Investigator. The participant should be advised to contact the Investigator immediately if there is any worsening of symptoms or if further systemic signs or symptoms develop. Antihistamines, topical corticosteroids, or antipruritic agents may be prescribed.

Participants with Grade  $\geq 3$  allergic reactions that are considered to be possibly or probably related to the study drug should permanently discontinue the CAB LA + RPV LA regimen and the participant should be withdrawn from the study. Participants should be treated as clinically appropriate and followed until resolution of the AE.

#### **7.4.5.12. Abacavir Hypersensitivity Reaction (ABC HSR)**

The most significant toxicity associated with ABC is the well-characterized drug-related hypersensitivity reaction (HSR). A detailed clinical description of this reaction (including the type and severity of events that can occur on re-challenge or reintroduction following ABC interruption for non-HSR reasons) and guidance regarding its management are included in the Local Country Prescribing Information for EPZICOM. Investigators must familiarize themselves with this information on ABC HSR in the Local Country Prescribing Information for each of these products prior to initiating participants on ABC therapy.

Studies have shown that carriage of the *HLA-B\*5701* allele is associated with a significantly increased risk of a HSR to ABC. In the prospective study CNA106030 (PREDICT-1), the use of pre-therapy screening for the presence of *HLA-B\*5701* and subsequently avoiding ABC in *HLA-B\*5701* positive patients, significantly reduced the incidence of clinically suspected ABC HSR from 7.8% (66 of 847) to 3.4% (27 of 803) ( $p < 0.0001$ ). In clinical studies EPZ108859 (ARIES) and CNA109586 (ASSERT), 0.8% (4/515) and 3.1% (6/192) of participants who were *HLA-B\*5701* negative and who received ABC developed a clinically suspected ABC HSR, respectively.

**In any participant treated with ABC, the clinical diagnosis of suspected HSR (as detailed in the Local Country Prescribing Information) must remain the basis of clinical decision making. Regardless of *HLA-B\*5701* status, it is important to permanently discontinue ABC and not re-challenge with ABC (i.e., ZIAGEN, EPZICOM/KIVEXA, TRIZIVIR, or TRIUMEQ) if a HSR cannot be ruled out on clinical grounds, due to the potential for a severe or even fatal reaction.**

#### **7.4.5.12.1. Essential Patient Information**

With reference to Local Country Prescribing Information and the ‘Participant Information and Consent Form’, Investigators must ensure that participants are fully informed regarding the following information on the hypersensitivity reaction prior to commencing ABC therapy:

- Participants must be made aware of the possibility of a hypersensitivity reaction to abacavir that may result in a life-threatening reaction or death and that the risk of a hypersensitivity reaction is increased in individuals who are *HLA-B\*5701* positive.
- Participants must also be informed that *HLA-B\*5701* negative individuals can also experience abacavir hypersensitivity reaction. Therefore, ANY participant who develops signs or symptoms consistent with a possible hypersensitivity reaction to abacavir MUST CONTACT their doctor IMMEDIATELY.
- Participants who are hypersensitive to abacavir should be reminded that they must never take any abacavir containing medicinal products (e.g., ZIAGEN, EPZICOM, KIVEXA, TRIZIVIR, or TRIUMEQ) again, regardless of their *HLA-B\*5701* status.
- In order to avoid restarting abacavir, participants who have experienced a hypersensitivity reaction should be asked to return any remaining EPZICOM / KIVEXA tablets to the Investigator or site staff.
- Participants, who have stopped abacavir for any reason, and particularly due to possible adverse reactions or illness, must be advised to contact their doctor before restarting EPZICOM / KIVEXA as more severe symptoms may recur within hours and may include life-threatening hypotension and death.
- Each participant should be reminded to read the Package Leaflet included in the EPZICOM / KIVEXA pack. They should be reminded of the importance of removing the Alert Card included in the pack, and keeping it with them at all times.

#### **7.4.5.12.2. Reporting of Hypersensitivity Reactions**

If a clinically suspected case of HSR to ABC meets one of the International Conference on Harmonization (ICH E2A, 1994 definitions of seriousness listed in Section 11.6.2 then, in addition to reporting the case as an SAE, the ABC HSR eCRF should also be completed within one week of the onset of the hypersensitivity reaction. Clinically suspected cases of HSR to ABC that do not meet criteria as an SAE can be recorded as an AE.

#### **7.4.5.13. Rash Without ABC HSR Symptoms**

**Including serious skin reactions such as Stevens-Johnson Syndrome, Toxic Epidermal Necrolysis, Erythema Multiforme or rash with significant liver dysfunction.**

Participants should be instructed to contact the Investigator as soon as possible if they develop a rash on study.

Participants who develop rash of any grade should be evaluated for the possibility of an ABC HSR or a serious skin reaction such as Stevens - Johnson syndrome (SJS), Toxic Epidermal Necrolysis (TEN) or Erythema Multiforme. SJS, TEN, and Erythema Multiforme have been reported very rarely in patients taking ABC-containing products. These patients generally do not have the cluster of additional symptoms (e.g., gastrointestinal and respiratory) that characterize the ABC HSR, but they do have features typical of these serious skin reactions.

If a serious skin reaction develops, ABC (and / or all other concurrent medication(s) suspected in the Investigators causality assessment) should be discontinued, and the participant should not be re-challenged with any ABC-containing medicinal product (i.e., ZIAGEN, TRIZIVIR, EPZICOM, or KIVEXA).

As many products other than abacavir also cause rash and/or serious skin reactions, all other medicinal products that the participant is receiving should also be reviewed and discontinued as appropriate.

The following guidance is provided for clinical management of participants who experience rash alone in the absence of accompanying diagnosis of ABC HSR, systemic or allergic symptoms or signs of mucosal or target lesions.

CAB is an analogue of DTG and mild to moderate rash is an expected adverse reaction for DTG-containing ART. Episodes generally occur within the first ten weeks of treatment, rarely require interruptions or discontinuations of therapy and tend to resolve within two to three weeks. No instances of serious skin reaction, including Stevens-Johnson syndrome (SJS), toxic epidermal necrolysis (TEN) and erythema multiforme, have been reported for DTG in clinical trials. For further characterization of HSR and rash observed with DTG-containing ART, please see the current version of the CAB IB .

Rash is an adverse drug reaction (ADR) for RPV. In clinical trials, most rashes emerged during the first 4 weeks of treatment, were transient, and usually mild (Grade 1) to

moderate (Grade 2). There were no Grade 4 rashes and none were serious. Treatment-related Grade 3 rash was reported in 0.1% of participants in the RPV group. Treatment-related rash led to permanent discontinuation in 0.1% of participants in the RPV group. No cases of erythema multiforme, SJS or TEN have been reported during clinical development of RPV.

Participants with an isolated Grade 1 rash may continue study drug at the Investigator's discretion. The participant should be advised to contact the Investigator immediately if there is any worsening of the rash, if any systemic signs or symptoms appear, or if mucosal involvement develops.

Participants may continue study drug for an isolated Grade 2 rash. However, study drug (and all other concurrent medication(s) suspected in the Investigators causality assessment) should be permanently discontinued for any Grade  $\geq 2$  rash that is associated with an increase in ALT. The participant should be advised to contact the physician immediately if rash fails to resolve (after more than two weeks), if there is any worsening of the rash, if any systemic signs or allergic symptoms develop, or if mucosal involvement develops.

Participants should permanently discontinue study drug [and all other concurrent medication(s) suspected in the Investigators causality assessment] for an isolated Grade 3 or 4 rash, except where the etiology of the rash has been definitively diagnosed as NOT attributable to study drug (see below), and the participant should be withdrawn from the study. Participants should be treated as clinically appropriate and followed until resolution of the AE. Every effort should be made to collect as much information as possible about the evolution of the event and any relationship with potentially related medical events (e.g., viral infection) or start of concomitant medication.

The rash and any associated symptoms should be reported as adverse events and appropriate toxicity ratings should be used to grade the events (based on DAIDS toxicity gradings – see Section 11.2, Appendix 2).

However, if the etiology of the rash has been definitively diagnosed as being unrelated to study drug and due to a specific medical event or a concomitant infection or a concomitant non-study medication, routine management should be performed and documentation of the diagnosis provided. In this situation, the study drug should be continued.

Participants in the Follow-Up Phase who are receiving ABC as part of their regimen should be evaluated for the possibility of a clinically suspected ABC HSR and managed appropriately as outlined in the local prescribing information for ABC.

**Any rash that is possibly related to study drug, and is present between Day 1 and The Week 4b visit for participants in the Oral Lead-in Phase, must be discussed with the Medical Monitor prior to initiation of CAB LA or RPV LA.**

Any participant receiving at least one dose of CAB LA and /or RPV LA who discontinue IP / Withdraw will initiate treatment with HAART and enter the LTFU Phase for 52 weeks of follow-up.

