## Dermatologic

PARAMETER	GRADE 1 MILD	GRADE 2 MODERATE	GRADE 3 SEVERE	GRADE 4 POTENTIALLY LIFE- THREATENING
Alopecia (scalp only)	Detectable by study participant, caregiver, or physician AND Causing no or minimal interference with usual social & functional activities	Obvious on visual inspection AND Causing greater than minimal interference with usual social & functional activities	NA	NA
Bruising	Localized to one area	Localized to more than one area	Generalized	NA
Cellulitis	NA	Non-parenteral treatment indicated (e.g., oral antibiotics, antifungals, antivirals)	IV treatment indicated (e.g., IV antibiotics, antifungals, antivirals)	Life-threatening consequences (e.g., sepsis, tissue necrosis)
Hyperpigmentation	Slight or localized causing no or minimal interference with usual social & functional activities	Marked or generalized causing greater than minimal interference with usual social & functional activities	NA	NA
Hypopigmentation	Slight or localized causing no or minimal interference with usual social & functional activities	Marked or generalized causing greater than minimal interference with usual social & functional activities	NA	NA
Petechiae	Localized to one area	Localized to more than one area	Generalized	NA
Pruritus  (without skin lesions)	Itching causing no or minimal interference with usual social & functional activities	Itching causing greater than minimal interference with usual social & functional activities	Itching causing inability to perform usual social & functional activities	NA
Rash Specify type, if applicable	Localized rash	Diffuse rash OR Target lesions	Diffuse rash AND Vesicles or limited number of bullae or superficial ulcerations of mucous membrane limited to one site	Extensive or generalized bullous lesions OR Ulceration of mucous membrane involving two or more distinct mucosal sites OR Stevens-Johnson syndrome OR Toxic epidermal necrolysis

 For pruritus associated with injections or infusions, see the *Site Reactions to Injections and Infusions* section

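### Section 7.4.5.13 names only abacavir in its stop and no-rechallenge rule for serious skin reactions, so the written default for stopping CAB and RPV is unclear for SJS and TEN and missing for low-grade erythema multiforme

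*Protocol*

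**What the plan says.** Protocol Section 7.4.5.13 (Rash Without ABC HSR Symptoms) states under its heading that it includes serious skin reactions, and it then gives two sets of instructions.

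**Serious skin reactions.** The stop rule is "If a serious skin reaction develops, ABC (and / or all other concurrent medication(s) suspected in the Investigators causality assessment) should be discontinued", followed by "the participant should not be re-challenged with any ABC-containing medicinal product". Because many products can cause such reactions, "all other medicinal products that the participant is receiving should also be reviewed and discontinued as appropriate". Neither CAB, RPV nor study drug is named in these instructions.

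**Graded rash guidance.** A scope sentence limits what follows to "rash alone in the absence of accompanying diagnosis of ABC HSR, systemic or allergic symptoms or signs of mucosal or target lesions". Within that scope:

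- Grade 2: "Participants may continue study drug for an isolated Grade 2 rash", although study drug stops permanently if a rash of Grade 2 or above comes with a rise in ALT.
- Grade 3 or 4: study drug is to be stopped permanently and the participant withdrawn "for an isolated Grade 3 or 4 rash, except where the etiology of the rash has been definitively diagnosed as NOT attributable to study drug". Where a specific unrelated cause is established, "In this situation, the study drug should be continued".

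The section refers investigators to the DAIDS table in Appendix 2 for grading.

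**The concern.** The two rules set different burdens of proof for study drug. For an isolated severe rash the default is to stop unless study drug is excluded as the cause. For a serious skin reaction the default, read literally, is to stop study drug only if it comes under suspicion. That order is backwards, since SJS and TEN are the worse events.

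The one product named is also one that a participant on CAB + RPV is not normally taking. The section itself ties abacavir use to participants in the Follow-Up Phase. The oral standard-of-care bridging allowed in Appendix 10 could in principle include abacavir as well.

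After the oral lead-in, the decision is whether to give another long-acting injection. Sections 7.4.7.4 and 11.11.4.1 say that both drugs can still be detected 12 months or more after injections stop, so a dose given while causality is unsettled cannot be taken back.

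**Working it through.** No arithmetic applies. The check sets the two rules side by side and then tests each named reaction against the Appendix 2 rash row.

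| | Serious skin reaction | Isolated Grade 3 or 4 rash |
|---|---|---|
| Product named in the stop rule | Abacavir | Study drug |
| Route to CAB and RPV | Investigator suspicion, or review and stop as appropriate | Automatic |
| What lifts the stop for study drug | No stop is set without suspicion or judgement | Cause definitively shown not to be study drug |
| Re-challenge | Barred for abacavir products only | Discontinuation is permanent |
| Withdrawal sentence | None attached | Yes |

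The parallel drafting is telling. The graded guidance twice adds a bracketed phrase about other suspected concurrent medication, each time directly after study drug. The serious-reaction rule uses nearly the same phrase but has abacavir in that position.

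**Does the Grade 3/4 rule reach these reactions anyway?**

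1. *SJS and TEN.* Appendix 2 (Dermatologic, Rash) lists both under Grade 4, so by grade the rule fits. But the scope sentence removes rash with systemic symptoms or with mucosal or target lesions, and the rule is written for an isolated rash. Appendix 2 itself builds mucosal disease into the higher grades: Grade 3 is a diffuse rash together with "Vesicles or limited number of bullae or superficial ulcerations of mucous membrane limited to one site", and Grade 4 includes ulceration at two or more mucosal sites. The grade points one way and the scope sentence the other. The result is ambiguous.
2. *Erythema multiforme.* It is not named in the rash row, and target lesions are Grade 2. If the scope sentence is applied, target lesions take the case out of the graded guidance and only the abacavir rule is left. If the scope sentence is ignored, the case is Grade 2 and study drug may continue unless ALT rises. Apart from that ALT case, neither reading gives a default to stop study drug. Should the case also meet the Grade 3 or 4 description, it shares the ambiguity in step 1.

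**Do other visible rules fill the gap?**

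- Section 7.4.5.11 stops CAB LA + RPV LA for Grade 3 or higher allergic reactions, but only when they are judged at least possibly related.
- Section 11.6.5 obliges the investigator to assess causality for study treatment, but sets no default when causality is unclear.
- The close of Section 7.4.5.13 requires discussion with the Medical Monitor of a possibly related rash during the oral lead-in before the first long-acting dose. It does not govern later doses.

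Each gives partial cover. None supplies the default that the isolated-rash rule has.

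**The case against.** The strongest reply is that the section should be read as a whole. Its heading takes in SJS, TEN and erythema multiforme, and it tells investigators to grade by DAIDS. If the scope sentence removed every mucosal or serious presentation, three of the four Grade 4 rash criteria (two-site mucosal ulceration, SJS and TEN, leaving only extensive bullous lesions) would drop out of a rule that expressly covers Grade 4. The coherent reading is then that SJS or TEN triggers the study-drug stop. This stands as a reasonable reading, and it is why the point for SJS and TEN is ambiguity rather than a plain omission. It does not help erythema multiforme graded on its target lesions.

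A second reply is that a stop depending on causality is not unusual here. Section 7.4.5.11 uses one for severe allergic reactions, a category in which Appendix 2 puts anaphylaxis at Grade 4. That is true, so conditionality alone is no fault. What remains is that two rules on skin reactions in one section differ, and the named product is not study drug.

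A reader might go further and infer that the protocol lets CAB and RPV continue through SJS or TEN, or permits re-challenge with them. The text does not support either inference. Suspected products are to be stopped, all others must be reviewed, and no visible text offers CAB or RPV re-challenge after a rash. Nor can one conclude that the protocol as a whole has no study-drug stop rule for these events. Part 1 is not shown. It contains the Section 5.5 withdrawal criteria and the Section 2.3.1 risk table, and the Amendment 5 change log shows that the latter has a mitigation entry for rilpivirine rash.

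**Conclusion.** The point holds as a wording defect confined to Section 7.4.5.13. The rule for the most serious skin reactions names a product outside the study regimen. For SJS and TEN it is unclear whether the firmer study-drug stop applies; for erythema multiforme graded on its target lesions, it does not apply on either reading.

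The practical size is small. The section reports none of the three reactions in rilpivirine development and no serious skin reaction in dolutegravir trials. It adds that rash with dolutegravir-containing therapy generally appears within the first ten weeks of treatment, so few long-treated participants would be affected. Nothing stops an investigator from discontinuing CAB and RPV, and no effect on the primary endpoint is claimed.

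The conclusion assumes that no passage in the part not shown overrides this section. A general stop rule there would reduce the point to an internal inconsistency. It remains worth correcting because the events can be fatal and the change is cheap.

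**What to change.** Replace the serious-skin-reaction sentence in Section 7.4.5.13 with one to this effect:

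*If a serious skin reaction develops, permanently discontinue study drug (CAB and RPV), any abacavir-containing product and all other suspected concurrent medication, and do not re-challenge with them. Study drug may continue only where a definitive diagnosis shows that it is not the cause.*

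The exception is the one the section already applies to isolated Grade 3 or 4 rash, so the two rules would carry the same burden of proof. Appendix 2 and the graded guidance can stay as they are.

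The cost is one sentence and no new assessments. The downside is that a rare participant who might otherwise have stayed on treatment, including one with low-grade erythema multiforme of unclear cause, would be taken off study drug. If that participant had received at least one long-acting dose, the section's closing instruction moves them to HAART and 52 weeks of long-term follow-up.
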